#### 7.3.6 Unscheduled Visit

Unscheduled visits may be required for example to evaluate a participant for a suspected AE or to evaluate for symptomatic possible disease progression requiring potential study termination and consideration of other treatments (e.g. symptomatic bony metastasis requiring radiation therapy). The visit will be documented as "Unscheduled Visit".

- Record adverse events as reported by participant or observed by investigator.
- Record vital signs, results of medical history, physical exam, height/weight, performance status (ECOG).
- Collect blood for hematology, biochemistry, coagulation (Section 7.2.1), AFP

#### If clinically indicated:

- MRI abdomen (or CT if not eligible), 3 phase IV contrast, liver
- CT chest (with or without IV contrast).
- Tumor objective response determination (RECIST v. 1.1).

### 7.3.7 Follow-Up Visits

The follow-up period will occur for at least every 3 months for 1 year after last study treatment dosage, even in patients who discontinue the study drug.

- Record survival status
- Record adverse events and concomitant medications as reported by participant or observed by investigator.
- Record vital signs, results of medical history, physical exam, height/weight, performance status (ECOG).
- Collect blood for hematology, biochemistry, coagulation (Section 7.2.1), AFP
- Record new anti-cancer treatment since last study visit, if applicable
- MRI abdomen (or CT if not eligible), 3 phase IV contrast, liver protocol.
- CT chest (with or without IV contrast).

Version: 11.0

Tumor objective response determination (RECIST v. 1.1).

# 7.4 Concomitant Medications, Treatments, and Procedures

All concomitant prescription medications taken during study participation will be recorded on the case report forms (CRFs). For this protocol, a prescription medication is defined as a medication that can be prescribed only by a properly authorized/licensed clinician. Medications to be reported in the CRF are concomitant prescription medications, over-the-counter medications and non-prescription medications.

#### 7.5 Prohibited Medications. Treatments, and Procedures

Treatment with oral steroids, calcineurin inhibitors, immune suppressive, other immune stimulatory, or anti-proliferative agents will not be permitted. Treatment with other chemotherapeutic agents will not be permitted. If participants are found to be taking such medications after entering treatment in the trial, then the participant will be recorded as an AE and undergo early termination from the trial.

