#### 4.2 Study Endpoints

#### 4.2.1 Primary Study Endpoints

The primary endpoint will be the ORR of the Nivolumab and BMS-986253 combination, and the ORR of the Nivolumab monotherapy. ORR will be determined based upon RECIST v. 1.1 criteria. The safety of BMS-986253 in combination with Nivolumab will be determined.

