# 7.7 Rescue Medications, Treatments, and Procedures

Corticosteroids may be provided at the discretion of the site clinical investigators as rescue therapy for high grade treatment related AEs (e.g. pneumonitis), usually 1-2 mg prednisone equivalents/kg/day and then tapered to off as AE resolves.

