# 8 Assessment of Safety

# 8.1 Specification of Safety Parameters

## 8.1.1 Definition of Adverse Events (AE)

An **adverse event** (AE) is any symptom, sign, illness or experience that develops or worsens in severity during the course of the study. Intercurrent illnesses or injuries should be regarded as adverse events. Abnormal results of diagnostic procedures are considered to be adverse events if the abnormality:

- · results in study withdrawal
- is associated with a serious adverse event
- is associated with clinical signs or symptoms
- leads to additional treatment or to further diagnostic tests
- is considered by the investigator to be of clinical significance

Version: 11.0

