#### 14.3 Protocol Deviations

A protocol deviation is any noncompliance with the clinical trial protocol, GCP, or Manual of Procedures (MOP) requirements. The noncompliance may be either on the part of the participant, the investigator, or the study site staff. As a result of deviations, corrective actions are to be developed by the site and implemented promptly.

These practices are consistent with ICH E6:

- 4.5 Compliance with Protocol, sections 4.5.1, 4.5.2, and 4.5.3
- 5.1 Quality Assurance and Quality Control, section 5.1.1
- 5.20 Noncompliance, sections 5.20.1, and 5.20.2.

All protocol deviations must be addressed in study source documents, reported to NYULH PCC CTO and BMS Program Official.

Protocol deviations must be reported to the local IRB per their guidelines. The site PI/study staff is responsible for knowing and adhering to their IRB requirements. All protocol deviations must be addressed in study source documents and reported to IRB Program Official at the time of annual continuing review. If a protocol deviation is determined to be reportable new information, the IRB will be notified immediately.

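### Section 7.5 has prohibited-medication use recorded as an adverse event, which adds entries that are not toxicities to the all-causality AE data

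*Combined protocol and SAP*

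**What the plan says.** Section 7.5 names classes of medication that are not permitted, among them oral steroids, other immune-suppressive agents and other chemotherapy. If a participant is found to be taking one after entering treatment, "then the participant will be recorded as an AE and undergo early termination from the trial". The sentence does not mention a protocol deviation.

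Section 8.1.1 defines an adverse event as "any symptom, sign, illness or experience that develops or worsens in severity during the course of the study". A bulleted list follows, which includes leading to study withdrawal, but its lead-in confines it to test results: "Abnormal results of diagnostic procedures are considered to be adverse events if the abnormality" meets one of the bullets.

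Section 14.3 states: "A protocol deviation is any noncompliance with the clinical trial protocol, GCP, or Manual of Procedures (MOP) requirements". It adds: "The noncompliance may be either on the part of the participant, the investigator, or the study site staff".

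Section 7.4 requires concomitant medications, prescription and non-prescription, to be entered on the CRF.

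Safety of the combination appears under the primary endpoints in Section 4.2.1 ("The safety of BMS-986253 in combination with Nivolumab will be determined") and again under the secondary endpoints in 4.2.2.

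**The concern.** An AE record should describe something that happened to the participant's health. The instruction in 7.5 creates one from a compliance finding. Sites that follow it will enter items with no natural severity grade and no resolution date, and nothing later in the protocol takes those items out again. The AE tables would then mix medical events with medication use, and a reader of those tables, including the DSMC, could not tell them apart without going back to the line listings. What is at stake is the cleanliness of the all-causality AE data in a trial that names safety among its primary endpoints and has only 25 participants per arm.

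**Working it through.** The plan states no figure on this point, so the check is mainly a comparison of sections.

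**1. Does medication use meet the AE definition?** Section 8.1.1 requires something that develops or worsens in severity. Starting or continuing a drug does neither. The early termination attached by 7.5 does not turn it into an AE, because the withdrawal bullet in 8.1.1 covers abnormal diagnostic results only.

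**2. Is there already a place to record it?** Yes, in two ways. Section 14.3 covers any noncompliance and expressly includes the participant's own. Section 7.4 captures the drug itself. Both apply by their own terms whether or not 7.5 refers to them, so the result of 7.5 is an additional record, not a lost deviation.

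**3. Can the AE record be completed sensibly?** Section 8.3 asks for severity, relationship and time of resolution. Section 8.2.2 requires every AE to be assessed for relationship, and its related category can be met by timing alone. An on-treatment medication entry could therefore be labelled related, and different sites could handle it differently.

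**4. Where does the record go?**
- Section 8.3 documents all on-study AEs whatever their relationship to treatment.
- Section 10.4.4 summarises safety endpoints by arm and compares their occurrence. It does not itemise them and has no rule that removes medication-use entries.
- Section 9.1 has the DSMC review cumulative AEs.
- Section 8.5 sends non-serious AEs to the drug supplier every three months.

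**5. Where does it not go?**
- The dose-limiting toxicity count in Section 5 needs a qualifying grade 3 or 4 toxicity attributed to treatment. Medication use is not a graded toxicity, so it is not counted.
- The halting rule in Section 8.9 counts grade 4 AEs, or AEs that call for permanent discontinuation, judged probably related. A medication entry is unlikely to qualify.

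**6. Scale.**
- Input: 25 participants per arm (Section 10.5).
- Shift in an arm's any-AE proportion = k/25, where k is the number of participants in that arm whose only AE record is medication use.
- For k = 1: 1/25 = 0.04, or 4 percentage points.
- The documents give no value for k. Over an assumed range of 0 to 3, the shift is 0, 4, 8 or 12 points (0/25, 1/25, 2/25, 3/25).
- For a participant who already has a true AE, the shift in this proportion is zero. Only the count of AE records rises, by one.

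**The case against.** The strongest reply is that this is a drafting slip with little consequence. The 7.5 sentence is garbled, since a participant cannot be an AE. The definition in 8.1.1 includes the broad word experience, and Section 8.1.2 gives drug overdose or abuse as an example of an important medical event, so the protocol does treat some drug-taking as AE material. Sections 7.4 and 14.3 remain in force, so nothing is lost.

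Much of this stands. There is no conflict between 7.5 and the deviation rule, and the surplus is only the AE entry. The argument from the definition is weaker: the requirement that the experience develop or worsen in severity still applies, and ordinary use of a listed drug is not an overdose.

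A reader might infer something stronger: that steroid use follows immune toxicity, so the arm with more toxicity would collect extra AE records and the primary safety comparison would be biased. The documents do not support that, for four reasons.
- The argument depends on whether steroids given for toxicity count as prohibited at all. Section 7.5 lists oral steroids without exception, while Section 7.7 says "Corticosteroids may be provided at the discretion of the site clinical investigators as rescue therapy" for high-grade treatment-related AEs. The table in Section 6.1.7 sets a dose and duration of prednisone beyond which treatment stops. That contradiction is a separate matter.
- A participant on steroids for a true toxicity already counts in any-AE incidence.
- AEs linked to withdrawal, where such an effect might be looked for, are not defined as an endpoint anywhere.
- No frequency by arm is given, so any assumed imbalance would be invented. For prohibited use unrelated to toxicity, the documents give no reason to expect one.

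**Conclusion.** The point holds as a small error in AE recording. The instruction in 7.5 does not fit 8.1.1, duplicates what 7.4 and 14.3 already provide, and lets entries that are not toxicities into AE data tabulated by arm. Its size is unknown. The figure of 4 percentage points per participant assumes full accrual of 25 in the arm, literal adherence to 7.5 and no other AE in that participant. The last condition will often fail in this population, and the effect is then confined to event counts and listings.

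The effect on the arm comparison is itself an inference, because 10.4.4 does not say which safety endpoints will be compared. It should not be read as a shown bias in the primary safety comparison or as a threat to the dose-limiting toxicity decision.

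**What to change.** In Section 7.5, replace the AE-recording instruction with: use of a listed medication is recorded as a concomitant medication (Section 7.4) and, where the use is prohibited, as a protocol deviation (Section 14.3); an AE is recorded only for any underlying medical event that meets Section 8.1.1. Add a matching CRF completion instruction. This changes recording only. It does not alter which medications are prohibited or when a participant stops treatment.

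Separately, reconcile Sections 7.5, 7.7 and the 6.1.7 table on corticosteroid use. The new deviation wording should follow the reconciled text, so that use it permits is not logged as a deviation.

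The cost is one protocol sentence, one CRF instruction, and a check before database lock for AE records already entered solely because of 7.5. Section 10.1 says a formal SAP will be completed before lock, so the handling of any such records can be stated there.

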#### 6.1.7 Dose Adjustments/Modifications/Delays

Recommendations for study drug modifications are provided in the tables below. The recommendations for Nivolumab monotherapy are from the Package Insert. Since no dose limiting toxicity has been observed for BMS-986253 monotherapy in phase I (Investigator Brochure) and the combination of Nivolumab and BMS-986253 is currently being evaluated in CA027-002 with no new safety signals noted,

Version: 11.0

the management plan for toxicity will be the same as for Nivolumab monotherapy however both agents will be withheld or discontinued based on the described AEs below.

There are no recommended dose modifications for hypothyroidism or hyperthyroidism.

Interrupt or slow the rate of infusion in patients with mild or moderate infusion reactions. Discontinue the study drug in patients with severe or life-threatening infusion reactions.

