# ADVERSE EVENT MANAGEMENT FOR NIVOLUMAB MONOTHERAPY OR FOR NIVOLUMAB IN COMBINATION WITH BMS-986253

Adverse Reaction	Severity*	Dose Modification
	Grade 2 diarrhea or colitis	Withhold dose a
Colitis	Grade 3 diarrhea or colitis	Withhold dose when single
		agent (Nivolumab
		monotherapy), Permanently
		discontinue when administered
		with additional study drug
	Grade 4 diarrhea or colitis	Permanently discontinue
Pneumonitis	Grade 2 pneumonitis	Withhold dose a
	Grade 3 or 4 pneumonitis	Permanently discontinue
	If AST/ALT is within normal	
	limits at baseline and increases	
	to more than 3 and up to 5 times	
	ULN	
Hepatitis	If AST/ALT is more than 1 and	Withhold dose b
	up to 3 times ULN at baseline	
	and increases to more than 5	
	and up to 10 times ULN	
	If AST/ALT is more than 3 and	
	up to 5 times ULN at baseline	
	and increases to more than 8	
	and up to 10 times ULN	
	If AST or ALT increase to more	Permanently discontinue
	than 10 times the ULN or total	
	bilirubin increases to more than	
	3 times the ULN	
Hypophysitis	Grade 2 or 3 hypophysitis	Withhold dose a
	Grade 4 hypophysitis	Permanently discontinue
Adrenal Insufficiency	Grade 2 adrenal insufficiency	Withhold dose a
	Grade 3 or 4 adrenal	Permanently discontinue
T 15:1 1 M 10:	insufficiency	145
Type I Diabetes Mellitus	Grade 3 hyperglycemia	Withhold dose a
	Grade 4 hyperglycemia	Permanently discontinue
Nephritis and Renal Dysfunction	Serum Cr more than 1.5 and up	Withhold dose a
	to 6 times the ULN	
	Serum Cr more than 6 times the	Permanently discontinue
	ULN	
Skin	Grade 3 rash or suspected	Withhold dose a
	Stevens-Johnson syndrome	
	(SJS) or toxic epidermal	
	necrolysis (TEN)	D " "
	Grade 4 rash or confirmed SJS	Permanently discontinue
- L PC	or TEN	Maria I I I I I
Encephalitis	New-onset moderate or severe	Withhold dose a
	neurologic signs or symptoms	

Version: 11.0

	Immune-mediated encephalitis	Permanently discontinue
	Other Grade 3 adverse reaction	Withhold dose a
	First Occurrence	
	Recurrence of same Grade 3	Permanently discontinue
	Adverse reactions	
	Life threatening or Grade 4	Permanently discontinue
	adverse reaction	
Other	Grade 3 myocarditis	Permanently discontinue
	Requirement for 10 mg per day	Permanently discontinue
	or greater prednisone or	
	equivalent for more than 12	
	weeks	
	Grade 2 or 3 adverse reactions	Permanently discontinue
	lasting 12 weeks or longer	

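### Section 7.5 bans steroids without exception and orders early termination, which contradicts the rescue steroids of 7.7 and the steroid stopping rule of 6.1.7

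*Combined protocol and SAP*

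**What the plan says.** Four parts of the protocol bear on what happens when a patient on study takes a steroid.

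- **7.5 (prohibited medications).** "Treatment with oral steroids, calcineurin inhibitors, immune suppressive, other immune stimulatory, or anti-proliferative agents will not be permitted". For a participant found on such a drug after starting treatment, "then the participant will be recorded as an AE and undergo early termination from the trial". The section has no exception and no cross-reference to 7.7 or 6.1.7.
- **7.7 (rescue).** "Corticosteroids may be provided at the discretion of the site clinical investigators as rescue therapy for high grade treatment related AEs", with the dose given as "usually 1-2 mg prednisone equivalents/kg/day and then tapered to off as AE resolves". Pneumonitis is its example. Neither the route nor the meaning of high grade is stated.
- **6.1.7 (dose modification).** In both arms the AE table decides: "both agents will be withheld or discontinued based on the described AEs below". One row, beginning "Requirement for 10 mg per day", requires permanent discontinuation when prednisone or equivalent at that dose or above is needed for more than 12 weeks. Other rows withhold drug, for example for "Grade 2 or 3 hypophysitis", Grade 2 adrenal insufficiency and Grade 2 pneumonitis. Footnote a, which prints below the 7.1.1 heading, restarts study drugs once the event is back to Grade 0 or 1. Footnote b does the same for hepatitis once AST/ALT is back to baseline.
- **8.1.1, 7.4 and 14.3.** These define an adverse event, require concomitant medications to be captured on the CRF, and treat non-compliance with the protocol as a deviation.

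**The concern.** The 6.1.7 table plainly expects steroids to be used on study. A limit tied to more than 12 weeks of use has almost no work to do if any oral steroid ends participation. Section 7.5 is nevertheless written as an unconditional ban with a mandatory consequence, and no section says which rule prevails. An investigator treating a toxicity therefore holds two instructions, and the two sites could resolve them differently.

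Two things are at stake. The first is study treatment: applied literally, 7.5 removes patients whom 6.1.7 would restart. The second is the safety record. Safety is part of the primary objective (3.1), and 10.4.4 compares safety endpoints between arms. If 7.5 is applied to a steroid given for a toxicity, the treatment of an event is entered as a further event.

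**Working it through.** The point rests on no figure in the plan, so there is nothing numerical to reproduce. The check puts the same patient through each rule.

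**Inputs.** The trigger and consequence are from 7.5, the permission and dose pattern from 7.7, and the withhold rows, steroid row and footnote a from 6.1.7.

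**Assumption.** High grade in 7.7 means Grade 3 or above; 7.7 does not define it.

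| Case | 6.1.7 | 7.5 read literally | 7.5 with 7.7 as an implied exception |
|---|---|---|---|
| A. First Grade 3 rash, rescue steroid, tapered off | Withhold, restart at Grade 0-1 | Terminate | Continue |
| B. Grade 2 pneumonitis, oral prednisone for less than 12 weeks | Withhold, restart at Grade 0-1 | Terminate | Terminate (not high grade) |
| C. Grade 2 adrenal insufficiency or Grade 2-3 hypophysitis, improved to Grade 0-1 on continuing oral replacement below 10 mg/day prednisone equivalent | Withhold, then restart | Terminate | Terminate (not tapered off; Grade 2 is also not high grade) |
| D. Grade 3 pneumonitis, rescue steroid | Permanently discontinue | Terminate | Permanently discontinue under 6.1.7 |

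1. Cases A to C each give opposite answers under 6.1.7 and literal 7.5.
2. The implied exception resolves A. It leaves B and C in conflict, because 7.7 covers only high grade events and describes a course that is tapered to nothing.
3. Case D shows no disagreement about study drug, since 6.1.7 has already stopped it.
4. Route does not rescue the text. Intravenous dosing would avoid the words about oral steroids, but 7.5 also bans immune suppressive agents, and corticosteroids are immune suppressive by any route.
5. For the AE instruction, 8.1.1 covers symptoms, signs, illnesses and experiences that appear or worsen on study. The toxicity that led to the steroid is already an AE under that definition. Taking the drug is not in itself one, and 7.4 already records it.

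**The case against.** The strongest reply is that 7.5 and 7.7 address different conduct. Section 7.5 concerns what a participant is found to be taking, which suggests unauthorised use. Section 7.7 concerns what an investigator chooses to give, and a specific rule normally prevails over a general one. Section 5.9.1 fits this reading, since it lists failure to adhere to protocol procedures among the withdrawal reasons. The steroid row in 6.1.7 also shows that the authors expected steroids on study. This stands as a reasonable reading and narrows the conflict. It is unwritten, however, and does not reach cases B and C.

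A reader might also infer more than the documents support:

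- **Arm imbalance.** For Grade 3 colitis, 6.1.7 reads "Withhold dose when single" agent but permanently discontinues in the combination arm, so extra stopping under 7.5 would fall on Arm 1. That difference between arms comes from 6.1.7 itself. Applying 7.5 to steroid-treated cases would stop both arms, so it does not show that 7.5 creates unequal handling.
- **Lost follow-up or power.** Section 7.3.5 continues follow-up of terminated participants, 7.3.7 schedules scans after the last dose, and 10.3 analyses all randomized participants.
- **Impact from counting table rows or comparing doses.** The number of withhold rows says nothing about how many patients need steroids. The rescue dose and the 6.1.7 limit are not comparable, because the limit needs both dose and duration.
- **A general allowance at or below 10 mg/day.** Exclusion 10 tolerates such doses at entry, but it is an entry criterion. A stricter rule on treatment is a legitimate choice.

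**Conclusion.** The contradiction is real and should be corrected, within limits. Read literally, 7.5 gives a disposition opposed to 6.1.7 for any patient given an oral steroid for a withheld event that 6.1.7 would restart. Read generously, the conflict narrows to steroids for withheld Grade 2 events and to physiologic or adrenal replacement. The narrowing assumes that high grade means Grade 3 or above. For replacement, it also assumes that the event has improved to Grade 0-1 and that the steroid stays outside the 6.1.7 row (below 10 mg/day, or not beyond 12 weeks). The instruction to record medication use as an AE is a separate, smaller fault that holds on either reading.

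The effect on treatment duration or AE counts cannot be sized from the documents. The conclusion is about consistent handling across sites and a clean safety record; it makes no claim about the ORR comparison.

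**What to change.** Add one exception to 7.5, for example: *except corticosteroids given to manage treatment-related AEs (6.1.7, 7.7) and physiologic or adrenal replacement; for these, 6.1.7 governs discontinuation.* State that exempt use is recorded as a concomitant medication under 7.4 and not as an AE. Replace the AE instruction for unauthorised use with a protocol deviation under 14.3.

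This leaves the 6.1.7 steroid row as it is, so replacement at 10 mg/day or more for more than 12 weeks would still stop drug. If that is not intended, 6.1.7 should say so.

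The cost is one wording amendment. Sample size, test, analysis set and visit schedule are unchanged, and the sections relied on already exist.
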